Complete physical examination including height and weight	Х					x				To be performed within 7 days before start of study intervention.
Directed Physical Examination		X	Х	Х	Х		Х	X		Conducted at all treatment visits.
Vital Signs (pulse rate, blood pressure)	Х	X	X	X	Х	Х	Х	X		Conducted at all treatment visits.
12-lead ECG	X									

Study Period	Screening Phase	Treatm (3-wee	ent/Interve k cycles)	ntion		EOT	Posttreatment			Notes
Visit Number/Title	Screening	Cycle 1	Cycle 2	Cycle 3	Cycle 4 onward	DC	Safety FU	FU Visits	Survival FU	
Scheduling window (days)	-42 to -1	+3	±3	±3	±3	At time of DC + 7 days	30 days from last dose + 14 days	Q16W ^a (±7 days)	Q12W (±7 days)	
Urine or Serum Pregnancy Test (WOCBP only)	х		X	X	х	x	x	x		Screening test must be performed within 24 hours for urine or within 72 hours for serum prior to first dose of study intervention.
HIV, hepatitis B and C screen	Х									Not required unless mandated by the local health authority.
Hematology and clinical chemistry laboratory assessment	x		x	x	X	x	x			Screening test must be performed within 7 days prior to first dose of study intervention. For all subsequent visits, laboratory assessments may be performed within 7 days prior to the visit.
PT/INR aPTT	x									Coagulation factors should be monitored closely throughout the study if participant is on anticoagulation therapy.

Study Period	Screening Phase	Treatm (3-wee	ent/Interverk k cycles)	ntion		EOT	Posttreatment			Notes
Visit Number/Title	Screening	Cycle 1	Cycle 2	Cycle 3	Cycle 4 onward	DC	Safety FU	FU Visits	Survival FU	
Scheduling window (days)	-42 to -1	+3	±3	±3	±3	At time of DC + 7 days	30 days from last dose + 14 days	Q16W ^a (±7 days)	Q12W (±7 days)	
TSH, T3/FT3, T4/FT4	х		Х		Х	X	х			T3/FT3 and T4/FT4 only required if TSH is abnormal. Thyroid function tests are to be repeated at alternate cycles after Cycle 4. Beginning with Cycle 2, participants may receive pembrolizumab or placebo while thyroid function tests are pending. Screening test must be performed within 7 days prior to first dose of study intervention. Subsequent tests may be performed within 7 days prior to the visit.
Urinalysis	х				See Note	x	х			Screening test must be performed within 7 days prior to first dose of study intervention. Repeat test every 6 cycles during treatment phase within 7 days prior to the visit.
AE/SAE review		X		←=			==→	X	Х	

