4 STUDY DESIGN

4.1 Overall Design

NOTE: Based on the data from an interim safety and efficacy analysis for KEYNOTE¬867 (data cutoff 11-JUN-2024), the eDMC recommended stopping the study since pembrolizumab in combination with SBRT did not demonstrate an improvement in EFS or OS, the study's primary endpoint and key secondary endpoint, respectively, compared to placebo plus SBRT, and the benefit/risk profile of the combination did not support continuing the trial. All prespecified interim analyses after IA1 and final analysis of the study described in the SAP will not be performed. Safety analysis will be performed at the end of the study; there will be no further pre-planned analyses for efficacy and ePRO endpoints collected from participants beyond the IA1 cutoff date of 11-JUN-2024.

In alignment with the study update memo sent to Investigators on 29-AUG-2024, all study participants must stop ongoing treatment with pembrolizumab/placebo. These participants must complete EOT visit followed by Safety Follow-up visit per protocol. All remaining study participants who have completed the safety reporting windows for AEs and SAEs per protocol must be discontinued from the study. All study participants will undergo unblinding at the end of the study. Investigators may apply for unblinding participants per protocol in the interim.

As of Amendment 08, information regarding ePRO assessments (EORTC QLQ-C30, EORTC QLQ-LC13, and EuroQoL EQ-5D-5L), biomarker samples (blood for genetic analysis, blood for ctDNA analysis, optional tumor sample), biopsies, and tumor imaging for BICR will no longer be collected. Tumor imaging, biopsies, and disease management should be performed per local SOC and Investigator's discretion. Efficacy data collection, including Follow-up and Survival Follow-up visits for efficacy will no longer be conducted. Safety reporting for AEs and SAEs must adhere to time windows per protocol. Updated analyses are described in Section 9.

This is a multisite, placebo-controlled, randomized, double-blind study designed to compare the efficacy and safety of SBRT + pembrolizumab versus SBRT + placebo in participants with unresected Stage I or II (N0, M0) NSCLC (AJCC 8th edition, Appendix 9). Eligible patients must have histologically or cytologically confirmed Stage I or II (N0, M0) NSCLC that has not been previously treated.

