Treatment with pembrolizumab or placebo control will continue until 17 cycles have been administered (approximately one year), or until disease recurrence, unacceptable adverse events, intercurrent illness that prevents further administration of treatment, death from any cause, investigator decision, or participant decision or withdrawal of consent, whichever occurs first.

Participants who discontinue for reasons other than disease recurrence, or where radiographic disease recurrence has not been verified by BICR, will have posttreatment follow-up imaging until disease recurrence is documented radiographically and verified by BICR, withdrawing consent, pregnancy, death, loss to follow-up or early study termination, whichever occurs first. Images will continue to be obtained even after initiating the new anticancer therapy if recurrence has not been documented or verified by BICR.

After the end-of-treatment, each participant will be followed for the occurrence of AEs and spontaneously reported pregnancy as described in Section 8.4.

All participants will be followed by telephone for OS until death, withdrawal of consent, or the end of the study.

Specific procedures to be performed during the study, including prescribed times and associated visit windows, are outlined in Section 1.3, Table 1 of the SoA. Details of each procedure are provided in Section 8.

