- Is a WOCBP and using a contraceptive method that is highly effective (with a failure rate of <1% per year) or be abstinent from heterosexual intercourse as their preferred and usual lifestyle (abstinent on a long-term and persistent basis), as described in Appendix 5 during the intervention period and for at least 120 days after last dose of pembrolizumab/placebo and 180 days after the last radiotherapy dose. The investigator should evaluate the potential for contraceptive method failure (ie, noncompliance, recently initiated) in relationship to the first dose of study intervention.
- A WOCBP must have a negative highly sensitive pregnancy test ([urine or serum] as required by local regulations) within 24 hours for urine or within 72 hours for serum before the first dose of study intervention.
- If a urine test cannot be confirmed as negative (eg, an ambiguous result), a serum pregnancy test is required. In such cases, the participant must be excluded from participation if the serum pregnancy result is positive.
- Additional requirements for pregnancy testing during and after study intervention are in Section 8.3.4.2.

- The investigator is responsible for review of medical history, menstrual history, and recent sexual activity to decrease the risk for inclusion of a woman with an early undetected pregnancy.
- Contraceptive use by women should be consistent with local regulations regarding the methods of contraception for those participating in clinical studies.

Informed Consent

- 9. The participant (or legally acceptable representative) has provided documented informed consent/assent for the study. The participant may also provide consent/assent for future biomedical research. However, the participant may participate in the study without participating in future biomedical research.
- 10. Has a radiation therapy plan approved by the central radiation therapy quality assurance vendor.

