8.3.4.2 Pregnancy Test

- Pregnancy testing:
 - Pregnancy testing requirements for study inclusion are described in Section 5.1.
 WOCBP require negative highly sensitive pregnancy test (urine or serum) within 24 hours for urine or within 72 hours for serum before first dose of study intervention. The definition of WOCBP is provided in Appendix 5. If a urine test is positive or not evaluable, a serum test will be required. Participants must be excluded/discontinued from the study in the event of a positive test result. Repeated pregnancy tests (such as monthly testing) must be performed prior to each study dose, and additional testing may be performed, as determined necessary by the investigator or required by local regulation, to establish the absence of pregnancy at any time during the participant's participation in the study. See Appendix 7 for further country-specific details.

MK-3475-867-08 FINAL PROTOCOL

- Pregnancy testing (serum as required by local regulations) should be conducted every treatment cycle (Q3W) during study intervention.
- Pregnancy testing (serum or urine as required by local regulations) should be conducted for the time required to eliminate systemic exposure after cessation of study intervention as described in Section 5.1.
- Additional serum or urine pregnancy tests may be performed, as determined necessary by the investigator or required by local regulation, to establish the absence of pregnancy at any time during the subject's participation in the study.

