8.4 Adverse Events, Serious Adverse Events, and Other Reportable Safety Events

The definitions of an AE or SAE, as well as the method of recording, evaluating, and assessing causality of AE and SAE and the procedures for completing and transmitting AE, SAE, and other reportable safety event reports can be found in Appendix 3.

Adverse events, SAEs, and other reportable safety events will be reported by the participant (or, when appropriate, by a caregiver, surrogate, or the participant's legally authorized representative).

The investigator and any designees are responsible for detecting, documenting, and reporting events that meet the definition of an AE or SAE as well as other reportable safety events. Investigators need to document if an SAE was associated with a medication error, misuse, or abuse.

Investigators remain responsible for following up AEs, SAEs, and other reportable safety events for outcome according to Section 8.4.3. The investigator, who is a qualified physician, will assess events that meet the definition of an AE or SAE as well as other reportable safety events with respect to seriousness, intensity/toxicity, and causality. Disease recurrence of the cancer under study is not considered an AE, as described in Section 8.4.6.

8.4.1 Time Period and Frequency for Collecting AE, SAE, and Other Reportable Safety Event Information

All AEs, SAEs, and other reportable safety events that occur after the participant provides documented informed consent, but before intervention allocation/randomization, must be reported by the investigator if the participant is receiving placebo run-in or other run-in treatment, if the event cause the participant to be excluded from the study, or is the result of a protocol-specified intervention, including, but not limited to washout or discontinuation of usual therapy, diet, or a procedure.

- All AEs from the time of intervention allocation/randomization through 30 days following cessation of study intervention must be reported by the investigator.
- All AEs meeting serious criteria, from the time of intervention allocation/randomization through 90 days following cessation of study intervention or 30 days following cessation of study intervention if the participant initiates new anticancer therapy, whichever is earlier, must be reported by the investigator.

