- All pregnancies and exposure during breastfeeding, from the time of intervention allocation/randomization through the time required to eliminate systemic exposure after cessation of study intervention as described in Section 5.1, or 30 days following cessation of pembrolizumab/placebo if the participant initiates new anticancer therapy must be reported by the investigator.
- Additionally, any SAE brought to the attention of an investigator at any time outside of the time period specified above must be reported immediately to the Sponsor if the event is considered related to study intervention.

Investigators are not obligated to actively seek AEs or SAEs or other reportable safety events in former study participants. However, if the investigator learns of any SAE, including a death, at any time after a participant has been discharged from the study, and he/she considers the event to be reasonably related to the study intervention or study participation, the investigator must promptly notify the Sponsor.

All initial and follow-up AEs, SAEs, and other reportable safety events will be recorded and reported to the Sponsor or designee within the time frames as indicated in Table 6.

Note: Country-specific differences are noted in Appendix 7.

Type of Event	Reporting Time Period: Consent to Randomization/ Allocation	Reporting Time Period: Randomization/ Allocation through Protocol- specified Follow- up Period	Reporting Time Period: After the Protocol- specified Follow-up Period	Time Frame to Report Event and Follow-up Information to Sponsor:
Nonserious Adverse Event (NSAE)	Report if: - due to protocol- specified intervention - causes exclusion - participant is receiving placebo run-in or other run-in treatment	Report all	Not required	Per data entry guidelines
Serious Adverse Event (SAE) including Cancer and Overdose	Report if: - due to protocol- specified intervention - causes exclusion - participant is receiving placebo run-in or other run-in treatment	Report all	Report if: - drug/vaccine related. (Follow ongoing to outcome)	Within 24 hours of learning of event
Pregnancy/ Lactation Exposure	Report if: - due to intervention - causes exclusion	Report all	Previously reported – Follow to completion/termination; report outcome	Within 24 hours of learning of event

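### The Amendment 08 close-out rule waits for the AE and SAE windows only, so a woman of childbearing potential can be discharged before her required pregnancy testing period ends

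*Combined protocol and SAP*

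**What the plan says.** The close-out sentence, "All remaining study participants who have completed the safety reporting windows for AEs and SAEs per protocol must be discontinued from the study", appears in Sections 1.1, 3, 4.1, 6.1 and 6.3.3. Section 8.4.1 sets the AE window at 30 days after cessation of study intervention. SAEs are reported "through 90 days following cessation of study intervention or 30 days following cessation of study intervention if the participant initiates new anticancer therapy", and the sooner of the two applies. For Germany, Appendix 7 (10.7.3) sets 120 days for SAEs.

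Pregnancy has its own period. Section 8.4.1 requires pregnancies to be reported "through the time required to eliminate systemic exposure after cessation of study intervention as described in Section 5.1", or for 30 days after the last pembrolizumab/placebo if new anticancer therapy starts. Section 8.3.4.2 says post-treatment testing "should be conducted for the time required to eliminate systemic exposure after cessation of study intervention as described in Section 5.1", with no exception for new therapy. Inclusion criterion 8 in Section 5.1 gives that period for WOCBP: "during the intervention period and for at least 120 days after last dose of pembrolizumab/placebo and 180 days after the last radiotherapy dose". Appendix 7 (10.7.2) asks EU sites to test monthly for as long as contraception is mandatory.

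Section 4.1 also keeps this commitment: "After the end-of-treatment, each participant will be followed for the occurrence of AEs and spontaneously reported pregnancy as described in Section 8.4". On visits, it says: "Efficacy data collection, including Follow-up and Survival Follow-up visits for efficacy will no longer be conducted".

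**The concern.** The discharge condition names two of the three reporting periods in Section 8.4.1. It cannot be read as covering the third, because Section 8.4.5 says that pregnancy is not considered an AE. Amendment 08 marks many superseded sections as kept for reference, but not 8.3.4.2 or 8.4.1, so the testing and reporting duties remain in force.

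A site that discharges a WOCBP when her SAE window closes cannot then complete the testing in 8.3.4.2. In the Schedule of Activities, the only visits after Safety Follow-up that carry a pregnancy test are the Follow-up visits, which Amendment 08 stops for efficacy. Section 8.4.1 adds that investigators need not actively seek reportable safety events in former participants. What is at stake is participant protection: late tests and site contact in a period the protocol still treats as needing them.

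**Working it through.** The plan states no figure for the gap, so there is none to reproduce. The check is day arithmetic with C1D1 as Day 1.

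**Inputs**
- Last infusion at cycle n: L = 1 + 21(n − 1), from the Q3W schedule without delay.
- Last radiotherapy day R: Day 7 (three fractions about every 3 days from C1D1) to Day 21 (start on C1D8, over at most 2 weeks), from 8.1.8.1.2.
- Cessation of study intervention: C = max(L, R), because Table 3 lists SBRT among the study interventions.
- SAE window closes at C + 90; in Germany C + 120; after new anticancer therapy C + 30.
- Section 5.1 period ends at max(L + 120, R + 180) if both limbs count, or L + 120 if only the drug limb counts.
- Gap = end of the Section 5.1 period minus close of the SAE window (0 if negative).

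**Worked cases, general rules, both limbs**
- n = 1, R = 21: L = 1, C = 21. max(121, 201) − 111 = 90.
- n = 1, R = 7: C = 7. max(121, 187) − 97 = 90.
- n = 4, R = 21: L = 64. max(184, 201) − 154 = 47.
- n = 5, R = 21: L = 85. max(205, 201) − 175 = 30. From here the drug limb always governs.
- n = 17: L = 337. 457 − 427 = 30.

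**Drug limb only**
- n = 1: 121 − 111 = 10 (R = 21) or 121 − 97 = 24 (R = 7).
- n ≥ 2: (L + 120) − (L + 90) = 30.

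| Gap in days, by cycle of last dose | 1 | 2 | 3 | 4 | 5 to 17 |
|---|---|---|---|---|---|
| General, both limbs, R = 21 | 90 | 89 | 68 | 47 | 30 |
| General, both limbs, R = 7 | 90 | 75 | 54 | 33 | 30 |
| General, drug limb only | 10 to 24 | 30 | 30 | 30 | 30 |
| Germany, both limbs, R = 21 | 60 | 59 | 38 | 17 | 0 |
| Germany, both limbs, R = 7 | 60 | 45 | 24 | 3 | 0 |
| Germany, drug limb only | 0 | 0 | 0 | 0 | 0 |

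**New anticancer therapy, general rules.** The SAE window closes 60 days sooner (C + 30 instead of C + 90), and the 8.3.4.2 period does not move. With both limbs the testing gap is 90 + 60 = 150 days at cycle 1 and 30 + 60 = 90 days from cycle 5. There is no reporting gap: pregnancy reporting then ends at L + 30, which is never later than C + 30.

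**Monthly tests, EU outside Germany, both limbs, no new therapy.** Taking a month as 30 days, the tests due after C + 90 are one (C + 120) from cycle 5 and three (C + 120, C + 150, C + 180) at cycle 1.

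**Sensitivity.** Giving the cycle 5 dose 3 days early leaves its gap at 30 days: L = 82, and max(202, 201) − 172 = 30.

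**The case against.** Several points on the other side have weight.

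- **No discharge day is set.** The sentence applies to participants who have completed the windows and does not say discharge happens on the closing day. A reader might infer that every WOCBP loses 30 to 90 days of cover. The text does not support that; the figures are maxima for discharge on that day.
- **The radiotherapy limb can be disputed.** Sections 8.3.4.2 and 8.4.1 refer to elimination of systemic exposure, and external-beam radiotherapy leaves no drug to eliminate. Both sections nevertheless point to Section 5.1, which joins the two limbs with *and*. The combined reading is better supported, but the drug-limb figures belong beside it.
- **The stopped Follow-up visits matter less than they seem.** They align with scans at Weeks 12, 28, 44, 60 and 76, nominally Days 85, 197, 309, 421 and 533. For last doses at cycles 5 to 17, the gap runs from L + 90 to L + 120. In 8 of those 13 cycles (7, 8, 9, 12, 13, 14, 15 and 17) no nominal visit falls in it. Testing there always rested on 8.3.4.2 and Appendix 7. The visits are also stopped only for efficacy, although discharge ends any visit.
- **Much protection remains.** A reader might infer that pregnancy reporting has been cancelled. It has not: the 8.4.1 duty stands, reporting is spontaneous by design, reported pregnancies are followed to completion under 8.4.5, and the contraception commitment continues.
- **The exposed group may be empty.** Counting back from the 29-AUG-2024 memo, only WOCBP with a last infusion after about 1 May 2024 (120 days) or last radiotherapy after about 2 March 2024 (180 days) were still inside the Section 5.1 period. The memo itself is not available and may contain pregnancy instructions.

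These points limit size and reach. They do not remove the conflict between the close-out sentence and 8.3.4.2. Nor was it necessarily moot: for a last infusion on the memo date at cycle 5 or later, the SAE window closes on 27-NOV-2024 and the testing period ends on 27-DEC-2024.

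**Conclusion.** The conflict is real but small. As written, the close-out rule allows, and on its face requires, discharge of a WOCBP before the testing and reporting period in 8.3.4.2 and 8.4.1 is over. The sizes in the table assume discharge on the day the SAE window closes, infusions every 21 days, radiotherapy ending between Day 7 and Day 21, and no new anticancer therapy. The 30-day gap from cycle 5 holds on either reading of Section 5.1 under the general rules; the 90-day figure needs the radiotherapy limb and a last dose at cycle 1. The 90 to 150 days after new therapy concern testing only.

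The documents give no count of WOCBP, so the practical reach is unknown. A reader might infer that the end-of-study safety analysis loses planned data. The documents do not support this: the AE and SAE windows are kept in full, and efficacy is also unaffected. The point makes no claim about male participants or their partners. It is worth considering as a participant-protection correction, with medium confidence.

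**What to change.** In each of the five places (1.1, 3, 4.1, 6.1 and 6.3.3), add to the existing AE and SAE condition: *and, for WOCBP, the pregnancy testing and reporting periods in Sections 8.3.4.2 and 8.4.1*. In 8.3.4.2, say whether testing, like reporting, ends at 30 days once new anticancer therapy starts.

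The cost is one repeated clause and one clarifying sentence. On the combined reading, a few WOCBP would stay on study about 30 to 90 days longer (0 to 60 in Germany), or up to 150 days longer after new therapy if no testing exception is added. The tests are ones the protocol already requires. There is no new procedure and no change to eligibility.

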4.2 Scientific Rationale for Study Design

SBRT and immunotherapy, such as pembrolizumab, are synergistic due to the immunogenic cell death caused by the former and the mechanism of action, efficacy, and favorable toxicity profile of the latter. Published studies have demonstrated the benefit and safety of chemoradiotherapy followed by the sequential administration of a checkpoint inhibitor for patients with NSCLC. The PACIFIC trial compared maintenance durvalumab to placebo in patients with unresectable Stage III NSCLC who had no evidence of disease progression following definitive chemoradiotherapy [Antonia, S. J., et al 2017] [Antonia, S. J., et al 2018]. Significant improvement in PFS and overall survival (OS) was obtained with an acceptable small increase in adverse events. In a secondary analysis of KEYNOTE-001, PFS and overall survival (OS) were significantly longer in patients with NSCLC treated with pembrolizumab who had previously received extracranial radiotherapy than in those patients who had not received extracranial radiotherapy [Shaverdian, N., et al 2017].

Treatment with pembrolizumab/placebo will be administered over a maximum of 17 cycles, consistent with other adjuvant trials within the pembrolizumab program. Additionally, as the participants in this trial will have significant comorbidities and would typically have minimal surveillance following SBRT (ie, "watchful waiting" consisting of 2 to 4 CT scans/year) as part of their standard of care, one year of pembrolizumab/placebo was seen as lowering the burden to participants as well as encouraging compliance with the visit schedule compared to the longer line-treatment plan of 2 years.

